## 7.2. Secondary Efficacy Endpoints and Analyses

Pharmacokinetics and pharmacodynamics are the secondary endpoints for the Phase 1b MAD part of the study and are described in Section 8. Efficacy will be evaluated for the Phase 1b MAD part of the study as an exploratory endpoint and details will be included in relation to the Phase 2 POC part of the study within this section.

### 7.2.1. Proportion of Patients with SRI-4 Response at Each Visit

The analyses described in Section 7.1.1, including sensitivity analyses allowing out of window assessment results (Sensitivity Analysis 2) and excluding patients with missing or out of window assessments (Sensitivity Analysis 3), will be repeated for each nominal visit and will be presented by study phase and treatment group in the FAS. The 3 components will not be summarized separately by visit.

A graphical display of SRI-4 response by study phase, treatment group, and visit in the FAS will be presented.

Statistical testing data will be omitted from MAD Phase 1b treatment group displays.

### 7.2.2. Proportion of Patients with SRI-5 Response at Each Visit

The SRI-5 is a composite index of SLE disease improvement that consists of scores derived from the SLEDAI-2K and the BILAG 2004 Index. Response based on the SRI-5 is defined by:

1)  $\geq$  5-point reduction from baseline in SLEDAI-2K global score

AND

2) No new severe disease activity (BILAG A organ score) or more than 1 new moderate organ score (BILAG B) compared with baseline

AND

3) No deterioration from baseline in the PGA by  $\geq$  30mm.

The analyses described in Section 7.1.1, including sensitivity analyses excluding patients with missing or out of window assessments (Sensitivity Analysis 3), will be repeated for each nominal visit based on the SRI-5 response definition and will be presented by study phase and treatment group in the FAS. The 3 components will not be summarized separately by visit for SRI-5 response.

Sponsor: Boston Pharmaceuticals, Inc.  
Protocol Number: BOS161721-02  
SAP Version and Date: Version 2.0, 29Nov2018

Statistical testing data will be omitted from MAD Phase 1b treatment group displays.

### 7.2.3. Proportion of Patients with SRI-6 Response at Each Visit

The SRI-6 is a composite index of SLE disease improvement that consists of scores derived from the SLEDAI-2K and the BILAG 2004 Index. Response based on the SRI-6 is defined by:

1)  $\geq$  6-point reduction from baseline in SLEDAI-2K global score

AND

2) No new severe disease activity (BILAG A organ score) or more than 1 new moderate organ score (BILAG B) compared with baseline

AND

3) No deterioration from baseline in the PGA by  $\geq$  30mm.

The analyses described in Section 7.1.1, including sensitivity analyses excluding patients with missing or out of window assessments (Sensitivity Analysis 3), will be repeated for each nominal visit based on the SRI-6 response definition and will be presented by study phase and treatment group in the FAS. The 3 components will not be summarized separately by visit for SRI-6 response.

Statistical testing data will be omitted from MAD Phase 1b treatment group displays.

### 7.2.4. Proportion of Patients with a sustained reduction of oral corticosteroid (CS) between Day 120 and Day 210

The proportion of patients with a sustained reduction of oral corticosteroid, defined as  $\leq$  10 mg/day and  $\leq$  Day 0 dose, between Day 120 and Day 210 will be summarized by study phase and treatment group in the FAS. LOCF and imputation for missing values will not be performed. Otherwise, statistical methods described in Section 7.1.1 will be implemented.

Statistical testing data will be omitted from MAD Phase 1b treatment group displays.

#### 7.2.5. Proportion of new BILAG A flare or >1 BILAG B flare relative to baseline through Day 210

The proportion of new BILAG A flare or >1 BILAG B flare relative to baseline through Day 210 will be summarized by study phase and treatment group in the FAS. Statistical methods described in Section 7.1.1 will be implemented, including LOCF methods within a body system. The analyses will also be repeated in observed data only (no LOCF). A BILAG A flare is defined as a new A score in at least one body system when compared to baseline. A BILAG B flare is defined as a new B score in at least two body systems at the same assessment when compared to baseline. BILAG grading is collected at each protocol specified visit as an assessment of “the past 4 weeks”. As such, the BILAG grade will be compared to baseline and the most recent prior assessment, as appropriate, to determine a new flare. The proportion of new BILAG A flare or >1 BILAG B flare relative to baseline will be summarized overall and by nominal visit.

Statistical testing data will be omitted from MAD Phase 1b treatment group displays.

Observed results will be presented in separate data listings for BILAG SLE history, BILAG-2004 index, and BILAG grading for all randomized patients.

#### 7.2.6. Proportion of patients with PGA worsening

The PGA is used to assess investigator’s general impression on the patient’s overall status of SLE disease activity via visual analogue scale (100 mm) with 0 being “very good, asymptomatic and no limitation of normal activities” with 100 mm being “most severe possible disease ever seen in all SLE patients.” The proportion of patients with PGA worsening, defined as an increase of >30mm from baseline, will be summarized by study phase and treatment group in the FAS overall and by nominal visit. Statistical methods described in Section 7.1.1 will be implemented, including LOCF methods. The analyses will also be repeated in observed data only (no LOCF).

Statistical testing data will be omitted from MAD Phase 1b treatment group displays.

PGA observed results will be presented in a data listing for all randomized patients.

#### 7.2.7. Proportion of patients with BICLA response

The BICLA is a responder index developed to measure response to therapy, and it includes scores from the BILAG, SLEDAI-2K, and PGA. BICLA response is defined as:

- 1) at least 1 gradation of improvement in baseline BILAG 2004 scores in all body systems with moderate disease activity at entry (e.g., all B [moderate disease] scores falling to C [mild], or D [no activity])

AND

Sponsor: Boston Pharmaceuticals, Inc.  
Protocol Number: BOS161721-02  
SAP Version and Date: Version 2.0, 29Nov2018

2) no new BILAG A or more than 1 new BILAG B scores

AND

3) no worsening of total SLEDAI-2K score from baseline

AND

4)  $\leq 10\%$  deterioration in PGA score

AND

5) no medication failure.

LOCF and imputation for missing values will not be performed. Otherwise, statistical methods described in Section 7.1.1 will be implemented. The analyses will be repeated overall and for each nominal visit based on the BICLA response definition and will be presented by study phase and treatment group in the FAS.

Statistical testing data will be omitted from MAD Phase 1b treatment group displays.

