### 3. STUDY DESIGN

#### 3.1. Study Design and Population

This is a Phase 1b/2 combined, randomized, multicenter, double-blind, placebo-controlled trial to study the clinical efficacy, safety, and pharmacokinetics (PK) of subcutaneously (SC) doses of BOS161721 in adult patients with moderately to severely active SLE. After successfully

Sponsor: Boston Pharmaceuticals, Inc.  
Protocol Number: BOS161721-02  
SAP Version and Date: Version 2.0, 29Nov2018

completing a screening phase, eligible patients will be randomized to a specified dose of BOS161721 or placebo. The dosing schedule will be monthly.

The trial will consist of 2 double blinded- portions: MAD Phase 1b and POC Phase 2. Patients may receive a total of 7 SC monthly doses of study drug on Days 0, 30, 60, 90, 120, 150, and 180, followed by safety/efficacy follow-up visit at Days 210, and safety follow up visits at Days 240, and 270.

SLE disease activity assessment data will be centrally reviewed by medical monitor and sponsor to ensure the scores are clinically meaningful and compliant with specific definition. The scope of responsibility includes, but is not limited to, review and confirmation of “A” and “B” British Isles Lupus Assessment Group (BILAG) system organ disease, confirmation of clinical components of the SLE Disease Activity Index 2000 (SLEDAI-2K) score at screening and during the study, and cross validation- of the instruments used in this study to assess the disease activity. Further details on the content and methods of data reports by the medical monitor and sponsor will be outlined in the Medical Data Review Plan along with the processes and procedures that will be followed.

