## 7. EFFICACY

### 7.1. Primary Efficacy Endpoint and Analyses

Safety is the primary endpoint for the Phase 1b MAD portion of the study and is discussed in Section 9. Efficacy will be evaluated for the Phase 1b MAD portion of the study as an exploratory endpoint and details will be included in relation to the Phase 2 POC portion of the study within this section.

#### 7.1.1. The proportion of patients with a SRI-4 response at Day 210

The primary efficacy endpoint is the proportion of patients who achieve a SRI-4 response at Day 210.

The SRI-4 is a composite index of SLE disease improvement that consists of scores derived from the SLEDAI-2K and the BILAG 2004 Index. Response based on the SRI-4 is defined by:

1)  $\geq$  4-point reduction from baseline in SLEDAI-2K global score

AND

Sponsor: Boston Pharmaceuticals, Inc.  
Protocol Number: BOS161721-02  
SAP Version and Date: Version 2.0, 29Nov2018

2) No new severe disease activity (BILAG A organ score) or more than 1 new moderate organ score (BILAG B) compared with baseline

AND

3) No deterioration from baseline in the PGA by  $\geq 30\text{mm}$ .

The proportion of patients who achieve a SRI-4 response at Day 210 will be presented and assessed using Pearson's chi-square test. The number of SRI-4 responders, treatment difference versus placebo, odds ratio, and 90% confidence interval will be displayed. The 90% confidence interval will be calculated with Wilson (score) confidence limits for the binomial proportion by treatment group. If any of the expected cell counts are less than 5, Fisher's exact test will be used and exact confidence intervals will be constructed. The analyses will be repeated for each of the three components contributing to the SRI-4 response. The primary analysis of the primary efficacy endpoint will be performed in the FAS and presented by treatment group. The analysis will be repeated in the PP analysis set.

The superiority of BOS161721 relative to placebo will be evaluated. If the proportion of SRI-4 responders for the selected POC dose in BOS161721 arm is higher than that of the placebo arm, then BOS161721 will be considered superior to placebo if the 2-sided p-value is less than 0.10.

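### In SAP v2.0, BICLA criterion 1 does not cover organs graded A at entry, so a stable patient with A and no B can be counted as a responder without any improvement

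*SAP*

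**What the plan says.** SAP v2.0, Section 7.2.7, defines BICLA response by five conditions joined by AND; v1.0 has the same text.

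1. "at least 1 gradation of improvement in baseline BILAG 2004 scores in all body systems with moderate disease activity at entry", with the illustration "e.g., all B [moderate disease] scores falling to C [mild], or D [no activity"
2. "no new BILAG A or more than 1 new BILAG B scores"
3. "no worsening of total SLEDAI-2K score from baseline"
4. at most 10% "deterioration in PGA score"
5. "no medication failure"

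The severity labels are fixed in Section 7.1.1, where the second SRI-4 component reads "No new severe disease activity (BILAG A organ score) or more than 1 new moderate organ score (BILAG B) compared with baseline". So A is severe and B is moderate. Section 7.2.5 counts an A as new by comparison with baseline. Section 3.1 describes the trial as one of "BOS161721 in adult patients with moderately to severely active SLE" and has both A and B organ disease confirmed by central review. BICLA is listed among the secondary efficacy endpoints in Section 2.2 and is analysed in the FAS.

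The latest SAP in the file is v3.0 of 13 November 2020. Its Section 7.2.7 lies in the part that is not shown.

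**The concern.** Criterion 1 is the only one of the five that asks for improvement, and it looks only at organs with moderate activity. In the SAP's own vocabulary that leaves out organs graded A. The rule is then stricter on moderate than on severe disease: an unchanged B blocks response and an unchanged A does not. For a patient who enters with A organs and no B, nothing in the definition requires improvement, and a stable course can be scored as a response. That misclassifies patients in an index meant to measure response to therapy. The BICLA rate in each arm would then mix improvement with mere stability.

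**Working it through.** The plan gives no figure for this point, so there is none to reproduce. The check has two parts.

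**Part 1: the rule applied to BILAG profiles.** The five criteria were applied to two-organ profiles with SLEDAI-2K and PGA unchanged and no medication failure. A B was counted as new only if the organ was C or D at baseline. Criterion 1 was read literally (B organs only) and then extended to A and B organs.

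| Entry grades → visit grades | Criterion 1 on B only | Criterion 1 on A and B |
|---|---|---|
| A/D → A/D | responder | non-responder |
| A/C → A/C | responder | non-responder |
| A/A → A/A | responder | non-responder |
| A/B → A/B | non-responder | non-responder |
| A/B → A/C | responder | non-responder |
| B/D → B/D | non-responder | non-responder |
| B/B → B/B | non-responder | non-responder |
| C/D → C/D | responder | responder |

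In the first three rows no organ is graded B at entry, so criterion 1 has nothing to test. The persisting A is not new, so criterion 2 is met, and criteria 3 to 5 are met by an unchanged patient. The other criteria still bite: the A/D patient becomes a non-responder if SLEDAI-2K rises by 1, PGA worsens by 11%, a new A appears, or a medication failure occurs. The last row shows that criterion 1 is equally empty for a patient with neither A nor B, under either reading.

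**Part 2: can the effect on the comparison be sized?** Only under assumptions that the SAP does not supply.

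- Patients: 132 in the FAS at 2:1 (Section 3.3), so 132 × 2/3 = 88 vs 132 × 1/3 = 44.
- Assumed true BICLA rates: p = 50% on drug and 30% on placebo.
- f: share of patients entering with A and no B. Not given; varied over 5, 10, 20 and 30%.
- s: share of those patients who meet criteria 2 to 5. Not given; varied by arm.

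Rate under the literal rule = (1 − f) × p + f × s. For f = 10% and s = 80% in both arms, the drug rate is 0.9 × 50% + 0.1 × 80% = 53% and the placebo rate is 0.9 × 30% + 0.1 × 80% = 35%. The difference shrinks from 20 to 18 points.

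Power of Pearson's chi-square at two-sided 10%, by exact enumeration of 88 vs 44 and counting only results in favour of the drug, is 71.1% with no affected patients. With affected patients it is:

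| s, drug vs placebo | f = 5% | f = 10% | f = 20% | f = 30% |
|---|---|---|---|---|
| 80% vs 80% | 66.6% | 62.1% | 53.2% | 44.6% |
| 60% vs 60% | 66.8% | 62.4% | 53.4% | 44.4% |
| 80% vs 60% | 70.7% | 70.4% | 70.1% | 69.9% |
| 70% vs 40% | 72.8% | 74.5% | 77.7% | 80.7% |

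With equal stability in the two arms, power falls. With a 20-point stability advantage for the drug it hardly moves, and with a 30-point advantage it rises.

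**The case against.** The strongest objection is that the text is superseded. The wording is from v2.0 and v1.0, and v3.0 may already have repaired it. This stands. Nor does the silence of v3.0 Section 11 on BICLA help. That section also omits the change of the log-rank test from one-sided (v2.0, Section 7.2.12.2) to two-sided (v3.0, same section). It likewise omits the change of medication failure from censored (v2.0, Section 7.2.15) to event (v3.0, Table 5). Its silence is no evidence either way.

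Second, patients with A and no B at entry may be rare. Section 7.2.10 of v2.0 ties moderately to severely active disease to a SLEDAI-2K of 6 or more, which does not imply an A organ, and the entry criteria are in the protocol. Central review shows that A grades are foreseen, not how often they occur without a B. This also stands: f could be close to zero.

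Third, the illustration is introduced as an example and so is not exhaustive. That carries less weight, because the criterion itself says moderate and the SAP reserves that word for B.

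A reader might infer that every patient with an A organ is a responder by default. That is too strong: a patient who also has a B organ must improve it, and criteria 2 to 5 must be met in every case. A reader might also infer that the rule necessarily dilutes the treatment difference and costs power. The loss follows only if stability is assumed about equal in both arms; a drug that also prevents worsening could leave power unchanged or increase it.

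**Conclusion.** The defect holds for the text of v2.0 and v1.0, as a misclassification in a secondary endpoint. A stable patient with A and no B at entry can be scored a BICLA responder with nothing improved, and a patient with A and B can respond with the A organ unchanged. This rests on the SAP's own labels for A and B and on a persisting A not being new.

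Its size is unknown. The share of such patients is not given, and neither the size nor the direction of the effect on the treatment difference can be stated. The power figures above are illustrations under assumed rates, not estimates for this trial. The primary SRI-4 analysis and the sample size based on it are unaffected. Whether the governing definition still has the gap can be settled only from Section 7.2.7 of v3.0.

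**What to change.** Check Section 7.2.7 of v3.0. Unless it already does so, reword criterion 1 to require at least one grade of improvement in all body systems graded A or B at entry: every A falling to B, C or D, and every B falling to C or D. State alongside it that an A falling to B is not a new B; otherwise two A organs that both improve to B could fail criterion 2. Keep the FAS as the analysis set, and report by arm how many patients have neither A nor B at entry, since criterion 1 tests nothing in them.

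The cost is one change of wording and one derivation from BILAG grades that are already collected. The downside is slightly lower reported BICLA rates.

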#### 7.2.8. Cutaneous Lupus Erythematosus Area and Severity Index (CLASI)

The CLASI is a comprehensive tool for assessment of disease activity and damage in cutaneous lupus, shown to be valid, reliable, and sensitive to changes in disease activity.

The total activity score will be calculated by summing the scores on the left side of the form (erythema, scale/hypertrophy, mucous membrane, alopecia – recent hair loss and clinically not obviously scarred).

The total damage score will be calculated by:

- (1) Sum the responses for “Dyspigmentation” in all anatomical locations
- (2) If a response for “Report duration of dyspigmentation after active lesions have resolved” is “Dyspigmentation usually lasts at least 12 months”, then multiply the sum in #1 by 2.
- (3) If a response for “Report duration of dyspigmentation after active lesions have resolved” is “Dyspigmentation usually lasts less than 12 months”, then the sum in #1 will not change.
- (4) If the sum in #1 is 0 and a response for “Report duration of dyspigmentation after active lesions have resolved” is missing, then the sum in #1 will not change.
- (5) Determine the Dyspigmentation Score based on the results from 2, 3, or 4.
- (6) Sum the remaining scores on the right side of the form (scarring/atrophy/panniculitis, alopecia - scarring of the scalp judged clinically).

(7) Sum the scores from #5 and #6 to obtain the total damage score.

If the total activity score or total damage score cannot be calculated, the total activity score or total damage score will be imputed using the LOCF method described in Section 5.5. If one of the total scores can be calculated and the other cannot, LOCF will be implemented for only the total score which cannot be calculated. If any individual scores which contribute to the total activity score or the total damage score, the total score in question will not be calculated and LOCF methods for total score will be implemented. LOCF methods will be implemented for CLASI response analyses only.

A sensitivity analysis for CLASI response will also be performed in the FAS excluding patients with missing CLASI results within a visit. If one or both of the total activity score or total damage score are missing at a visit, the patient will not be included in the response analysis at that visit. LOCF methods will not be implemented for the sensitivity analysis.

The mean and standard deviation of the change from baseline in CLASI total activity and total damage scores will be presented graphically over time by study phase and treatment group.

#### 7.2.8.1. Proportion of patients with CLASI response

CLASI response is defined as 50% improvement from baseline in “A” (total activity) or “B” (total damage) scores. This assessment will be applied to all patients as all are required to have cutaneous disease activity.

The analyses described in Section 7.1.1 will be repeated overall and for each nominal visit based on the CLASI response definition and will be presented by study phase and treatment group in the FAS.

Statistical testing data will be omitted from MAD Phase 1b treatment group displays.

#### 7.2.8.2. Results and Changes from Baseline in CLASI

The analysis of CLASI total activity score and CLASI total damage score will be performed separately using an analysis of covariance (ANCOVA) model with change from baseline to each nominal visit as the dependent variable, treatment group as the factor, and the corresponding baseline CLASI score as a covariate. The p-value for the difference between the BOS161721 and placebo groups at each nominal visit is based on the F-test.

Descriptive statistics for the activity score and damage score will be summarized separately at baseline and each visit. Change from baseline will be summarized at each post-baseline visit. The LS Mean estimate, its standard error and 90% CI will be tabulated by treatment group and for the difference between treatment groups (BOS161721 versus placebo) for change at each visit. Missing CLASI results will not be imputed. Observed results only will be presented for the change from baseline analysis.

Statistical testing data will be omitted from MAD Phase 1b treatment group displays.

Sponsor: Boston Pharmaceuticals, Inc.  
Protocol Number: BOS161721-02  
SAP Version and Date: Version 2.0, 29Nov2018

CLASI observed results will be presented in data listings for all randomized patients.

#### 7.2.9. Results and Changes from Baseline in Swollen and Tender Joints ACR-28

The ACR-28 joint count evaluates the number of tender and swollen joints in the shoulder, elbow, wrist, hand, knee joints. Joints of the feet are excluded.

The analysis of Swollen and Tender Joints ACR-28 for the sum of tenderness (left and right) and the sum of swelling (left and right) will be performed separately using an analysis of covariance (ANCOVA) model with change from baseline to each nominal visit as the dependent variable, treatment group as the factor, and the baseline ACR-28 score as a covariate. The derived sum for tenderness and swelling is calculated and provided in the clinical database. A missing total sum of swelling or sum of tenderness will not be imputed. Observed results only will be presented for the change from baseline analysis. The p-value for the difference between the BOS161721 and placebo groups at each nominal visit is based on the F-test.

Descriptive statistics for the tenderness and swelling derived sums will be summarized separately at baseline and each visit. Change from baseline will be summarized at each post-baseline visit. The LS Mean estimate, its standard error and 90% CI will be tabulated by treatment group and for the difference between treatment groups (BOS161721 versus placebo) for change at each visit.

The mean and standard deviation of the change from baseline in ACR-28 sum of tenderness and sum of swelling will be presented graphically over time by study phase and treatment group.

Statistical testing data will be omitted from MAD Phase 1b treatment group displays.

Swollen and Tender Joints ACR-28 observed results will be presented in data listings for all randomized patients.

